9.2 Statistical Methods

For each cohort, the planned analyses will include descriptive statistics on the proportions of responses (% subjects with partial or complete response), cumulative incidence of response with death considered to be a competing risk and the time to complete response. The response probabilities, including complete response probability and partial response probability, will be estimated using the sample proportions, and their inferences, including confidence intervals and hypotheses testing, will be evaluated using Binomial distributions. Survival analysis will include methods based on Kaplan-Meier estimates and Cox regression. Although we have a small sample size, if it is appropriate, we will consider additional analyses for the primary and secondary endpoints using the analysis of variance, multiple regression and logistic regression models. Graphical tools will be used to display the appropriate estimates (i.e. estimated proportions and Kaplan-Meier curves) and their corresponding 95% confidence intervals.

Results for each cohort will be compared separately to the historical data from the large numbers of patients treated at the NIH previously with either a single or repeat course of immunosuppression from prior NHLBI studies: the h-ATG/CsA protocol (90-H-0146); the h-ATG/CsA vs. Cytoxin/CsA protocol (97-H-0117); the h-ATG/CsA/MMF protocol (00-H-0032); the h-ATG/CsA/Rapamune protocol (03-H-0193); the r-ATG vs. alemtuzumab protocol (03-H-0249); and h-ATG/CsA vs. r-ATG/CsA protocol (06-H-0034). More specifically, results from the current trial will be compared to our large historical experience with a horse ATG based regimen in nearly 400 patients (from the aforementioned studies) of a hematologic response rate of 60-70%, a complete response rate of 10-15%, a relapse rate of 30-40%, a clonal evolution rate (any clonal abnormality) of 15-20%, and a high risk evolution rate (to monosomy 7, high risk MDS, leukemia, or complex cytogenetics) of 10-15%.

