9.3 Primary Endpoints

The primary objective of this phase I/II study is to evaluate the safety and activity profile of h-ATG/CsA/eltrombopag in treatment naïve SAA.

- The primary safety endpoint will be toxicity profile in the 6 months following h-ATG/CsA/eltrombopag.
- The primary efficacy endpoint is CR rate at 6 months (see section 7 for CR definition).

Subjects who drop out, who have failed to respond and opt for alternative therapy (e.g. bone marrow

transplant), or who require eltrombopag to be restarted (cohort 2 only) before the 6-month evaluation will be counted as non-responders.

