9.6 Off Study/Off Treatment Criteria

Subject choice: Subjects may withdraw from the study at any time. The risks of withdrawing will be discussed, as will alternative treatment options. The subject will be informed that his/her condition poses a high mortality rate. The risks of not receiving further therapy include a high mortality rate with supportive care only. Those subjects who choose to withdraw will be strongly encouraged to continue to have blood counts monitored until initiation of alternative SAA therapy or through the 6 month off study medication to assess for late occurring adverse events.

Principal investigator decision: Should any of the following events occur, study drug administration will be discontinued. The subject will be followed until resolution of the event and laboratory values monitored through 6 months or until initiation of alternative SAA therapy:

- Intolerance of eltrombopag not resolved by dose reduction
- Thrombosis/embolism (DVT, PE, stroke or TIA, myocardial infarction) other than central line thrombosis
- Persistent hepatotoxicity as defined in section 5.3
- Infusion-related h-ATG reactions refractory to all appropriate supportive measures
- Life threatening acute hypersensitivity reactions
- Pregnancy or unwillingness to refrain from pregnancy
- Initiation of additional immunosuppressive therapy other than steroids or cyclosporine (if beyond 6 months then mycophenolate mofetil can also be administered per PI discretion in patients who cannot tolerate cyclosporine and who require immunosuppression) or if beyond 2 years, sirolimus per protocol 17-H-0019
- Evidence of a clonal disorder identified in subjects with super severe baseline neutropenia (ANC < 200/ μ L) who were not initially excluded because cytogenetics was not available or pending.

There are risks to pregnancy for patients with aplastic anemia or a history of aplastic anemia, and it is generally advised against, regardless of participation in a research trial. For this protocol, if pregnancy occurs when a patient is not actively receiving medical drugs, it will not be cause for withdrawal from study.

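### Section 9.2 names only death as competing with response and gives no estimator for time to complete response, so the descriptive curves can sit above the 9.3 proportion when failures leave for transplant

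*Combined protocol and SAP*

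**What the plan says.** Section 9.2 lists three descriptive items for each cohort: the response proportions, and then "cumulative incidence of response with death considered to be a competing risk and the time to complete response". No competing event other than death appears, no estimator is attached to time to CR, and no censoring rule is given. Section 9.2 also says "Survival analysis will include methods based on Kaplan-Meier estimates and Cox regression", and it lists Kaplan-Meier curves among the displays.

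The response probabilities themselves follow another route: "The response probabilities, including complete response probability and partial response probability, will be estimated using the sample proportions", with their inference, "including confidence intervals and hypotheses testing, will be evaluated using Binomial distributions".

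Section 9.3 states "The primary efficacy endpoint is CR rate at 6 months". Its non-responder rule opens with "Subjects who drop out, who have failed to respond and opt for alternative therapy (e.g. bone marrow", goes on to cohort 2 subjects who need eltrombopag restarted, and ends "before the 6-month evaluation will be counted as non-responders".

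Section 9.6 says that, for subjects whose study drug the investigator stops, follow-up includes "laboratory values monitored through 6 months or until initiation of alternative SAA therapy". Section 7 excludes improvement that depends on growth factors or transfusion from counting as response; it does not mention improvement after transplant. Section 9.4 plans response at 3 and 12 months and yearly afterwards.

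**The concern.** A subject who fails and goes to transplant has left because of non-response. Section 9.3 foresees this and scores the subject as a failure. The curves in 9.2 have no matching rule. In a standard competing-risks analysis, a subject whose observation stops without the event or a listed competing event is censored. Censoring credits that subject with the later response chance of those still at risk, although the subject left because treatment had failed. If counts after transplant are used instead, the count-based criteria in section 7 could score engraftment as response to the study regimen.

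The same cohort could then have two 6-month answers: a proportion under 9.3 and a higher curve under 9.2. This matters because the study is single-arm, and 9.2 sets each cohort against historical rates (response 60-70%, CR 10-15%). After month 6 even the 9.3 rule no longer applies, while response is still assessed.

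**Working it through.** **1. The plan's own figure.** Section 9.1 gives a two-stage design with 24 then 7 subjects, stopping at 2 or fewer CRs and accepting the null at 6 or fewer of 31, for CR rates of 10% against 30%. The rejection probability is the sum over x = 3 to 24 of P(X1 = x) × P(X2 ≥ 7 − x), with X1 binomial on 24 and X2 binomial on 7. At 30% this gives 0.8651, against the stated 0.865. At 10% it gives 0.0305, within the 0.05 limit. These use CR counts only, so nothing below changes them.

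**2. Set-up for the curves.** Section 7 assesses response at months 3 and 6, so a two-landmark calculation is enough.
- n = 31: cohort size, section 9.1.
- r3 and r6: first responses at months 3 and 6. Assumed.
- t: non-responders transplanted between the landmarks. Not in the documents; assumed 0 to 5.
- No deaths and no other censoring. Assumed, to isolate the effect.

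**3. Formulas.**
- Transplant as a competing event: (r3 + r6)/n. Here this equals the 9.3 proportion.
- Transplant censored: 1 − (1 − r3/n) × (1 − r6/(n − r3 − t)).
- Difference: r6 × t / [n × (n − r3 − t)].

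**4. Complete response, r3 = 5 and r6 = 5.** The proportion is 10/31 = 32.3%. For t = 1, the censored curve is 1 − (26/31)(20/25) = 32.9%. For t = 5 it is 1 − (26/31)(16/21) = 36.1%.

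| Transplanted | Proportion | Curve if censored | Gap (points) |
|---|---|---|---|
| 0 | 32.3% | 32.3% | 0 |
| 1 | 32.3% | 32.9% | 0.6 |
| 2 | 32.3% | 33.6% | 1.3 |
| 3 | 32.3% | 34.4% | 2.1 |
| 5 | 32.3% | 36.1% | 3.8 |

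**5. Overall response depends on when responses occur.** With 20 responses by month 3 and 5 more at month 6, the proportion is 25/31 = 80.6%, and the gap runs from 1.6 points (t = 1) to 13.4 points (t = 5). If all 25 respond by month 3, r6 = 0 and the gap is zero for every t. Section 2.9.1 supports the second pattern: all of the 11 responses among 13 subjects were seen by month 3. CR is different, because section 2.9.2 describes cohort 2 counts as maintained or normalised between months 3 and 6, which leaves room for later CRs.

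**The case against.** The strongest objection is that 9.2 is silent rather than wrong. That is largely fair, and it rules out several stronger readings.

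- A reader might infer that time to CR is assigned to Kaplan-Meier. The text ties Kaplan-Meier and Cox to survival analysis and attaches no method to time to CR.
- A reader might infer that transplanted failures are censored by rule. No such rule is written. An analyst who carried the 9.3 rule over to the curves would keep them at risk as never-responders to month 6, and no overstatement would follow. The clause in 9.6 concerns follow-up after investigator-decided discontinuation, and its list of reasons does not include non-response or transplant. It makes loss of counts plausible but is not an analysis rule.
- A reader might infer that the bias is always upward. It needs responses after the departures; with none, curve and proportion coincide.
- A reader might infer that the trial's CR result is overstated. The primary endpoint and its test use binomial proportions under the 9.3 rule.

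The size is also open to challenge. Section 4 enrols subjects who lack a suitable sibling donor or are not transplant candidates, and section 2.3.1 notes the time needed to find an unrelated donor, so early transplants may be few. One subject in 31 is 3.2 points, and the standard error of a 30% proportion is √(0.3 × 0.7/31) = 8.2 points.

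What remains is that 9.2 does specify a method, with one named competing event. Only an unwritten step brings it into line with 9.3, and that step covers nothing after month 6.

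**Conclusion.** The point holds for the descriptive cumulative-incidence and time-to-CR curves only. As 9.2 stands, these curves can exceed the 9.3 proportion if subjects who fail and take alternative therapy are censored and others respond later, or if counts after transplant are accepted.

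Under the assumed 1 to 5 transplants among 31 and the CR timing in step 4, the 6-month CR curve is about 0.6 to 3.8 points too high. With no transplants the gap is zero. Overall response is little affected if nearly all responses come by month 3, as the interim data in section 2.9.1 suggest. The effect after month 6 is not quantified, because the documents give neither transplant counts nor later CR timing. This is a cheap improvement, not a threat to the primary conclusion.

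**What to change.** In section 9.2:
- Name death, transplant and other alternative therapy for SAA as competing events for both response and complete response.
- Name the cumulative-incidence (Aalen-Johansen) estimator for both.
- Disregard counts after transplant or alternative therapy, including after month 6.
- Keep dropouts and cohort 2 eltrombopag restarts before month 6 as non-responders instead of censoring them. Without this, the curve can still differ from the 9.3 proportion even once transplant is a competing event. Because a cohort 2 subject may respond at month 3 and then relapse, say also whether that earlier response counts on the curve; if it does, the curve measures first response and need not match the 6-month proportion.

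The cost is one sentence and a recoding of events at analysis. It needs no new data and no further subjects. The curves may come out slightly less favourable.

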Severe aplastic anemia (SAA) is a life-threatening bone marrow failure disorder characterized by pancytopenia and a hypocellular bone marrow. Allogeneic bone marrow transplantation offers the opportunity for cure in younger patients, but most are not suitable candidates for transplantation due to advanced age or lack of a histocompatible donor. Comparable long-term survival in SAA is attainable with immunosuppressive treatment with horse anti-thymocyte globulin (h-ATG) and cyclosporine (CsA). However, of those patients treated with h-ATG/CsA, one quarter to one third will not respond, and 30-40% of responders relapse. The majority of the hematologic responses observed following initial h-ATG/CsA are partial, with only a few patients achieving normal blood counts. Furthermore, analysis of our own extensive clinical data suggests that poor blood count responses to a single course of ATG (non-robust responders), even when transfusion-independence is achieved, predicts a worse prognosis than when robust hematologic improvement is achieved (protocol 90-H-0146). The explanation for partial recovery and relapse are not fully understood, but incomplete elimination of auto-reactive T cells and insufficient stem cell reserve are both possible. Furthermore, 10-15% of SAA patients treated with standard immunosuppression will develop an abnormal karyotype in follow-up, with monosomy 7 being most common, which portends progression to myelodysplasia and leukemia. In contrast, malignant clonal evolution is rare in complete responders to immunosuppression. Although horse ATG/CsA represented a major advance in the treatment of SAA, refractoriness, incomplete responses, relapse, and clonal evolution limit the success of this modality. Thus, newer regimens are needed to address these limitations, and provide a better alternative to stem cell transplantation.

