Cyclosporine (CsA) is a major immunosuppressive drug and probably secondary only to corticosteroids in worldwide utilization in this role. In addition to its longstanding use in bone marrow and solid organ transplant recipients; CsA has been widely employed as an immunosuppressive drug in many autoimmune diseases. In contrast to ATG, CsA has a selective inhibitory effect on T lymphocytes, suppressing early cellular response to antigenic and regulatory stimuli. By blocking expression of nuclear regulatory proteins, it leads to reduced T cell proliferation and activation with diminished release of cytokines such as interleukin-2 and interferon- γ . CsA binds to intracellular receptors termed immunophilins, inhibiting in turn the activity of calcineurin, which results in the blocking of interleukin-2 production and T cell activation and proliferation. *In vivo*, CsA inhibits the release of IL-2 from activated T-cells and consequently decreases T cell proliferation.^{24,25}

h-ATG/CsA is the current standard immunosuppressive regimen in SAA.¹ The addition of CsA to ATG improved response rates to 60-70% and the 5-year survival in responding patients to 80-90%.²⁶⁻²⁸ With this regimen, relapses occur in 1/3 of responders and clonal evolution to myelodysplasia and leukemia in 10-15% of cases overall.¹ Although this non-transplant therapy represents a therapeutic success, the significant minority of unresponsive patients, frequent relapse, and progression to late clonal disease remain problematic and result in significant morbidity and mortality. Robust and rapid hematologic recovery has

been associated with better survival outcomes,²⁷ and in our experience, complete hematologic responders are unlikely to evolve to myelodysplasia or leukemia (unpublished data).

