Marrow biopsies were performed at study entry, at the 12-week response assessment, and for responders at one year after study entry. Supplemental Figure 4 shows pre-treatment and one-year biopsies. There is striking normalization of cellularity in three of four responders. There was no increase in reticulin on 12-week biopsies in any patient, and no increase in fibrosis in follow-up marrows at 6 or 12 months in responders remaining on the extension phase.

Of the 14 non-responders, two patients died of disease progression, from complications of severe cytopenias. Two patients showed morphologic changes and cytogenetic abnormalities (monosomy 7) consistent with progression to myelodysplasia; one patient ultimately died, and the other underwent allogeneic stem cell transplantation. Progression to monosomy 7/MDS is concerning, given the controversy regarding whether chronic G-CSF increases progression to MDS in SAA as summarized above, and the warning regarding progression of MDS to AML for patients being treated with an alternative TPO-mimetic, romiplostim. Of note, romiplostim directly binds to the thrombopoietin receptor (c-mpl) and competes with endogenous thrombopoietin; while eltrombopag binds to a transmembrane domain of c-mpl leading to signal transduction. The distinct mechanism of action between the 2 thrombopoietin mimetics may account for differences in efficacy and safety profiles between them. In our cohort of over 400 patients with SAA followed long-term, approximately 15% progress to clonal disease including myelodysplasia and leukemia, and therefore two patients out of 25 enrolled is not unexpected. Our experience also suggests that patients with long-standing severe refractory disease and who lack of a robust response to initial immunosuppression, as were enrolled on our protocol, are the most likely to progress.

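### Section 9.2 compares a trial followed for at most 60 months with historical clonal-evolution rates that carry no follow-up time

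*Combined protocol and SAP*

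**What the plan says.** - Section 9.2 compares each cohort separately with earlier in-house studies. Its specific yardstick is "our large historical experience with a horse ATG based regimen in nearly 400 patients". The rates listed include "a clonal evolution rate (any clonal abnormality) of 15-20" per cent and "a high risk evolution rate (to monosomy 7, high risk MDS, leukemia, or complex cytogenetics) of 10-15" per cent. No time point is attached to either.
- The précis states that "10-15% of SAA patients treated with standard immunosuppression will develop an abnormal karyotype in follow-up".
- Section 2.3.2 gives "clonal evolution to myelodysplasia and leukemia in 10-15% of cases overall".
- Section 2.6 reports: "In our cohort of over 400 patients with SAA followed long-term, approximately 15% progress to clonal disease including myelodysplasia and leukemia". It uses that rate to judge the pilot study: "therefore two patients out of 25 enrolled is not unexpected".
- Section 7 defines three outcomes separately: PNH (more than 1% GPI-deficient neutrophils), myelodysplasia or leukemia (WHO criteria), and clonal hematopoiesis (a new marrow cytogenetic abnormality at a landmark visit). Section 9.4 groups PNH, a chromosomal clone, morphologic myelodysplasia and acute leukemia under one secondary endpoint.
- Section 9.4 follows subjects for up to 60 months, and section 9.6 ends participation after 5 years.
- Section 9.1, in the paragraph on the enlarged extension cohort, estimates clonal evolution by sample proportions with standard errors and confidence intervals. Section 9.2 provides a cumulative incidence with death as a competing risk, but names it only for response.

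**The concern.** A cumulative rate has meaning only with a time attached. The historical figures carry none: the précis speaks only of follow-up and section 2.6 only of long-term observation. The trial side is cut off at 5 years, and a raw proportion also counts subjects with shorter follow-up as event-free. If the historical patients were watched for longer, the benchmark is too high for the trial's window and an increase could go unseen. If they were watched for a shorter time, the error runs the other way.

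This matters because the trial has no concurrent control and clonal evolution is a leading late-safety question. Section 2.9.1 gives a lower risk of cytogenetic evolution as a reason for shortening eltrombopag in Cohort 2, and section 9.5 leaves clonal evolution out of the stopping rules. The historical comparison is therefore the main planned way to judge whether the rate has changed.

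There is a second, smaller problem: the event behind each rate is not fixed. Section 9.2 does not say what any clonal abnormality includes, and the précis range for an abnormal karyotype is the one that 9.2 assigns to high-risk evolution alone.

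**Working it through.** **1. The plan's own figure.** Section 9.1 assumes a clonal-evolution proportion of 21% and n = 32, and states a 97.6% probability of at least 3 cases. For X ~ Binomial(32, 0.21), P(X ≥ 3) = 0.9764, so the figure is reproduced. It is the only clonal-evolution figure that can be recomputed. The historical rates come without counts or times.

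**2. The historical rates side by side.**

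| Place | Event | Rate | Time |
|---|---|---|---|
| Section 9.2 | any clonal abnormality | 15-20% | none |
| Section 9.2 | high-risk evolution | 10-15% | none |
| Précis | abnormal karyotype | 10-15% | none |
| Section 2.3.2 | myelodysplasia and leukemia | 10-15% | none |
| Section 2.6 | clonal disease | about 15% | none |

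The 2.3.2 figure fits the high-risk line of 9.2, and the 2.6 figure lies in both ranges. The mismatch that remains is the précis karyotype rate against the any-abnormality rate of 9.2, which share only the value 15%.

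**3. What an undated rate implies at the trial's times.** Assume a constant hazard and a historical cumulative rate C reached at T years. The rate at t years is then 1 − (1 − C)^(t/T). The documents do not give T, so it is varied.

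| T (assumed) | C = 15%: at 2 y | at 5 y | C = 20%: at 2 y | at 5 y |
|---|---|---|---|---|
| 2 years | 15.0% | 33.4% | 20.0% | 42.8% |
| 5 years | 6.3% | 15.0% | 8.5% | 20.0% |
| 10 years | 3.2% | 7.8% | 4.4% | 10.6% |
| 15 years | 2.1% | 5.3% | 2.9% | 7.2% |

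Worked entry: C = 0.15, T = 10, t = 5 gives 1 − 0.85^0.5 = 0.078.

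**4. Size of the possible error.** If 15% was reached at 10 years, then 0.85 = exp(−10·h0). A trial rate of 15% at 5 years means 0.85 = exp(−5·h1), so h1 = 2·h0. The trial hazard would be double, yet both percentages would read 15%. In events by 5 years:
- Cohort of 31: 31 × 0.15 = 4.7 against 31 × 0.078 = 2.4.
- Extension cohort of 87: 87 × 0.15 = 13.1 against 87 × 0.078 = 6.8.

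**5. Whether this could change a reading.** Exact 95% confidence intervals, taking full 5-year follow-up for illustration:
- 5/31 = 16.1% (5.5% to 33.7%). This covers both 15% and 7.8%, so one cohort of 31 cannot tell them apart.
- 13/87 = 14.9% (8.2% to 24.2%). This covers 15% but not 7.8%, so the reading depends on the missing time.

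**The case against.** The strongest defence is that only section 9.2 prespecifies a comparator, while the précis and section 2.6 are background. Section 9.2 also commits to comparison with historical data from named in-house protocols, and it already separates any abnormality from high-risk evolution. Clonal evolution is one secondary endpoint with no stated test, the extension cohort is explicitly descriptive, and at 31 subjects a five-point difference is 31 × 0.05 = 1.6 events. Kaplan-Meier methods are mentioned in 9.2 and could be applied.

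Much of this stands, and it rules out several stronger readings:
- **A three-way contradiction.** A reader might infer that 9.2, the précis and 2.6 give three rival benchmarks. They do not: 15% belongs to both ranges, and an analyst following the plan would use 9.2.
- **A known bias from choosing 15-20%.** A reader might infer that the broader range tilts the result towards no increase. The endpoint in 9.4 is itself broad, and the documents do not show which rate is right, so that direction is not established.
- **A pooled significance test that flips with the benchmark.** The plan compares cohorts separately and sets no test or significance level for this endpoint, so p-values on all subjects together would describe an analysis that is not planned.
- **Leaving PNH out.** Section 9.4 lists PNH under clonal evolution, so dropping it would contradict the stated endpoint.

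The missing time is not answered. The sentence in 9.2 that makes the comparison specific gives undated ranges, and no time-to-event method is assigned to clonal evolution. A descriptive comparison still needs both sides measured over the same period.

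**Conclusion.** The point holds as a defect of time scale and event definition in the historical comparison. As written, a proportion observed over at most 5 years is set against rates of unknown duration. For a historical 15%, the matching 5-year rate is 7.8% if the rate was reached at 10 years and 15% if it was reached at 5 years. In the first case a doubled hazard would look like no change. The sample-proportion estimator is stated only for the extension cohort; for cohorts 1 to 3 none is named.

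The figures rest on an assumed constant hazard and assumed historical horizons. The direction of error is conditional: longer historical follow-up would hide an increase, and shorter would exaggerate one. The definitional part is limited to the précis karyotype figure and the unstated place of PNH. The effect is confined to a descriptive secondary comparison; the primary endpoint, sample size and stopping rules do not depend on it.

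**What to change.** In section 9.2, replace the two undated clonal-evolution ranges with cumulative incidence at fixed times, such as 2 and 5 years, with death as a competing risk, computed from the roughly 400 in-house historical patients. Give it separately for new cytogenetic abnormality, high-risk evolution and PNH, using the section 7 definitions for cytogenetic evolution and PNH and the 9.2 list for high-risk evolution. Estimate each trial cohort the same way at the same times, with confidence intervals, and make the section 9.1 estimator agree. Correct or explain the précis figure for an abnormal karyotype.

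The method is already in 9.2 for response, so it needs only to be extended. The cost is a re-tabulation of data the sponsor holds, one paragraph in 9.2 and small edits to 9.1 and the précis. No new data from trial subjects are needed.
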